### 4.3.7 Study Visit 6 (Post 12-Month Follow-Up)

- Administer CHW Caregiver Satisfaction Survey
- Administer Asthma Control Questionnaire
- 2-week parental recall of symptoms, school absences, and work days missed

### 4.3.8 Unscheduled Visits

Usual care includes the caregivers' ability to make clinical visits for their children whenever they feel that it is necessary. In addition, caregivers may contact the CHW for an unscheduled visit via cell phone for non-clinical issues to assist them in meeting their goals. CHW will assess goals on a case by case basis and make follow-up calls as needed. If the CHW is requested to accompany caregivers for unscheduled visits, the CHW will do their best to accommodate the caregivers' needs. CHWs are expected to contact families within 48 hours after receiving phone messages from families or patients to assess whether a home visit or a primary care office follow-up appointment is needed.

#### 4.4 School Intervention

### 4.4.1 Community Health Worker Coordination

The primary care CHW will contact the school CHW to identify newly consented children present in each West Philadelphia elementary school participating in the study during weekly team meetings. The primary care CHW will then be responsible for contacting the child's caregiver to arrange a visit for collection of appropriate forms and medications.

### 4.4.2 School Nurse Coordination

School CHW will:

- Provide a portable locked filing cabinet that can be stored in the school nurse's office for study participants
- Help school nurse with filing medication administration forms (med1 forms) and attaining asthma medications for study participants.

#### 4.4.3 Classroom Environmental Assessments

School CHW will:

- Visit participant classrooms to do an environmental assessment for asthma triggers within the first 2 weeks of enrollment in the study.
- Using environmental assessment findings, advise teacher of appropriate asthma trigger avoidance measures.
- Provide teacher with supplies to assist in decreasing asthma triggers in the classroom. Supplies may include white vinegar and a spray bottle for cleaning, electrostatic dust cloths (dusters), and storage bins. School CHW will notify appropriate school personnel of any pest problems identified in the classroom.

### 4.4.4 Open Airways for Schools Curriculum

Implementation of the Open Airways for Schools Curriculum will occur over three to six asthma management education sessions.

- The school CHW will conduct Open Airways for Schools classes at least once every semester for children with asthma facilitated by the school nurse or designated school staff by the principal.
- Classes with be separated into sessions by grade.

## 4.4.5 School Based Asthma Therapy

School Based Asthma Therapy (SBAT) involves the administration of controller or preventive asthma medication at school in addition to rescue asthma medication as needed. School CHW will coordinate with teachers/school administers for all children that attend a school with the asthma intervention and have a primary CHW. To do this, school CHW will:

- Schedule an initial intake for children receiving SBAT
- Utilize an MDI checklist for school nurse or school CHW to assess child's ability to self-administer his/her medication

- Schedule a time for the child to return to the school nurse's office for daily medication administration.
- Utilize a tracking system for the child's medication use (rescue and controller)

### 4.5 Rescue Medication Administration

Participants may use asthma rescue medication if there is an exacerbation in his/her asthma symptoms in the school, home and clinic as a part of their usual care.

# 4.6 Subject Completion/Withdrawal

Subjects may withdraw from the study at any time without prejudice to their care. They may also be discontinued from the study at the discretion of the Investigator for lack of adherence to study procedures. It will be documented whether or not each subject completes the clinical study. If the Investigator becomes aware of any serious, related adverse events after the subject completes or withdraws from the study, they will be recorded in the source documents and on the CRF.

Subjects who become a ward of the state during study participation will continue to have their medical records reviewed, but will no longer participate in study visits or the completion of questionnaires. The state agency assigned legal guardianship of the participant will be asked to provide consent for medical record review of the participant during the study follow-up period. If consent cannot be obtained the participant will be withdrawn.

In the event that a parent or legal guardian regains custody and a participant is no longer a ward of the state, the legal guardian may be approached to provide consent for study participation. Once consent has been obtained, study visits can resume for the duration of the follow-up period.

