### 3.1.2 Primary Care Based Intervention

Children who are randomized to the primary care arm will be assigned a primary care community health worker (CHW). We will implement the *Yes We Can*TM Children's Asthma Program  intervention which is a medical-social model based on a chronic care approach, including risk stratification, clinical care management, social care coordination by a community health worker, and primary care asthma champions. This intervention includes asthma education and trigger reduction visits and care coordination. There will be five clinic visits and four home visits over 12 months implemented by the *primary care CHW* who is integrated into the practice.

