Families of children who are not randomized to the primary care intervention will be offered Community Asthma Prevention Program (CAPP) asthma classes, conducted at community sites, which are available to the general public. Data will be collected from the control arm at 3, 6, 9 months by phone or in person. At 12 months an office visit will be scheduled, pulmonary function testing (spirometry) performed and end-of-study data collected. After completing the study these patients will receive one home visit from a primary care CHW to complete an asthma trigger assessment and distribute asthma trigger reduction supplies.

Schools who are not randomized to intervention arm will be offered training after the study data collection period has ended and during the last year of grant funding in how to implement the school asthma interventions and will be provided with information on how to sustain these interventions by obtaining reimbursement from health insurance companies for school CHW services.

During the COVID-19 pandemic, the study activities detailed above will be modified as follows to preserve the health and safety of participants, healthcare professionals, study staff and the West Philadelphia community. Data collection for study visits may take place remotely by telephone or video conference using a HIPAA-compliant application licensed by CHOP. In person clinic visits solely for study purposes will take place as permitted by CHOP Research Institute Policy and Guidelines. Study activities designed to take place in a school setting may take place remotely by telephone or video conference using a HIPPA-compliant application licensed by CHOP.

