Asthma control is the primary outcome of this study. Symptom-free days, and school absences are secondary outcomes in this study. Asthma control has been cited by the NAEPP guidelines and asthma outcomes workshop as an important goal for prevention of asthma morbidity. In several studies, poor asthma control, whether defined by the patient (using self-reported, validated instruments) or by national asthma guideline classifications, has been strongly associated with an increased risk of asthma exacerbations which may lead to emergency room visits, hospitalizations and even death. Asthma control will be measured using Juniper's Asthma Control Questionnaire, a validated instrument for children and adults. Symptom-free days will be based on parental report recall of the last two weeks, consistent with previous studies. School absences will be measured by school and parental report. Additional secondary outcomes will include asthma-related emergency

visits and hospital visits (obtained from CHOP EHR), and cost-savings. Moderator variables will be measured using the CARAT survey which is a Child Asthma Risk Assessment Tool designed to help clinicians, asthma counselors and parents determine potential risks for children with asthma.

Data will be collected for all individually randomized participants at baseline, 3, 6, 9 and 12 months by a member of the research team in person or by phone. Participants will be compensated \$25 for each visit with data collection at baseline, 3, 6, and 9 months and \$45 for the end of study visit at 12 months.

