# 4.6.1 Early Termination Study Visit

If participants withdraw prior to completing the study, all previously collected data will be stored and used for analysis.

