### 6.3.2 Efficacy Analysis

The primary analysis will be based on an intention to treat approach and will include all subjects randomized at Study Visit 1. The primary efficacy endpoint will be the change in asthma control between Study Visit 1 and Study Visit 5. Secondary efficacy endpoints will include the change in asthma symptom days and school absences between Study Visit 1 and Study Visit 5.

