5.3 Missing data

Missing data on covariates will be handled using formal multiple imputation as needed (Little 2002; 1992; Molenberghs 2007). The proposed mixed effects models make limited assumptions of "missing at random" (MAR). To the extent that children are lost to follow-up, we shall include in our models covariates that are associated with the probability of dropout, to limit confounding by dropout. We anticipate no school withdrawals. The primary analysis will be "as randomized" (also called intention to treat). Reporting will follow the CONSORT guidelines for randomized studies and cluster randomized designs. (Altman 2012; Elbourne and Campbell 2001).

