5.4 Dropout and switching

All analyses will follow the principles of "intention to treat" (as randomized) for both the school and child level randomizations (S+ vs S- and A+ vs A-). The following special rules apply for unusual situations.

(1) Child dropout or loss to follow-up

If a child leaves the study, his or her data will be captured and used until dropout. There will be no change in the A+ A- assignment.

(2) Child remains in the study but leaves a named school

If the child remains in the study but leaves a named school (cells a,b,c,d), she will be moved to the cells e or f as appropriate. This change in designation will not affect the contrast of A+ vs A-within a school designation. Data that accrues while the child is in cells a,b,c, or d will be linked to that school until the time of the switch for contrasts of S + vs S-.

After a switch from a,b,c or d, to e or f, the child-level observation will apply to the e and f cells.

(3) Child randomized while in e or f and moves into an enrolled school (cells a, b,c,d) then his or her follow-up is attributed to the e or f cell until the switch, and then to a,b,c or d cells thereafter. Both sets of longitudinal data can share the same baseline measures of outcome.

If this switch occurs, the child will be recoded separately according to the "S" allocation.

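### Children can be discontinued from the study for non-adherence with no provision for further outcome collection, which could bias the child-level (P+ v P-) contrast

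*Protocol*

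**What the plan says.** Protocol 4.6 lets families withdraw at any time and then gives the investigator a separate power: "They may also be discontinued from the study at the discretion of the Investigator for lack of adherence to study procedures". The discontinuation is from the study, not only from intervention activities. No threshold is set.

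On what follows, Protocol 4.6.1 carries a title that refers to an early termination visit but describes none. It says: "If participants withdraw prior to completing the study, all previously collected data will be stored and used for analysis". SAP 5.4 agrees: "If a child leaves the study, his or her data will be captured and used until dropout". It leaves the child-level assignment unchanged. Continued record review after study visits stop is spelled out in Protocol 4.6 only for children who become wards of the state.

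The analysis is by intention to treat. Protocol 6.3.2 states: "The primary analysis will be based on an intention to treat approach and will include all subjects randomized at Study Visit 1". It defines the primary endpoint as change in asthma control from Visit 1 to Visit 5 (12 months). For missing outcomes, SAP 5.3 relies on mixed models under missing at random (MAR) and adds: "we shall include in our models covariates that are associated with the probability of dropout".

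On schedules, Protocol 3.1.2 says of P+: "There will be five clinic visits and four home visits over 12 months". Protocol 3.1.3 says of the control arm: "Data will be collected from the control arm at 3, 6, 9 months by phone or in person". It adds a 12-month office visit with spirometry. For everyone it states: "Data will be collected for all individually randomized participants at baseline, 3, 6, 9 and 12 months".

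**The concern.** The decision to discontinue is taken after randomisation and depends on adherence, which may be related to outcome. It is made at the discretion of an investigator; Protocol 9.1.2 blinds the principal investigator only as far as is feasible. A discontinued child has no Visit 5 ACQ, so the promise to analyse everyone randomised cannot be met with observed 12-month data for that child.

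Two features make this more than a formality. First, P+ families have more scheduled activity to miss. Second, the SAP's own mediation hypotheses (Table 6.2.3) are that controller adherence and reaching care coordination goals lead to better child outcomes. On that reasoning, children removed for non-adherence would tend to be those expected to do worse. If such removals were concentrated in P+, the estimated benefit of the primary care community health worker would be too large.

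The MAR model may have little to work with. Home Visits 1 to 3 are due within 2, 4 and 6 weeks of enrolment, before the first follow-up ACQ at 3 months. A P+ child discontinued at that stage would contribute only a baseline score. SAP Table 5.1.2 lists no adherence covariate, and neither document plans an analysis under non-ignorable dropout. The SAP's sensitivity analyses cover numerical integration, pandemic timing and mediation. SAP 5.1.2 itself acknowledges that dropout can disturb the balance that randomisation achieved.

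**Working it through.** **Reproducing the plan's figure.** SAP 8 gives power for A+ v A- (the same contrast as P+ v P-) at an effect of 0.35 SD of change with no interaction: 0.95 at n=432 and 0.99 at n=600. I used SD 1, two-sided alpha 0.05 (sidedness is not stated, so this is assumed), equal arms and no design effect, because the contrast is within school.

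Power = Φ(0.35/√(2/m) − 1.96), where m is the number per arm.

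- m = 216: √(2/216) = 0.0962, and Φ(3.637 − 1.96) = 0.953. Stated: 0.95.
- m = 300: √(2/300) = 0.0816, and Φ(4.287 − 1.96) = 0.990. Stated: 0.99.

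Both reproduce, so 0.0962 SD is a fair standard error for judging bias at n=432.

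**Bounding the removal rate.** Protocol 3.3.2 expects at least 600 evaluable of 640, so 40/640 = 6.25% loss from all causes. If all 40 were in P+ (about 320 children), that would be 40/320 = 12.5% of P+.

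**Bias.** Suppose a share d of P+ and nobody in P- is discontinued, and the removed children have a 12-month change g SD worse than the retained children. The full P+ mean is (1 − d) × retained mean + d × removed mean. The retained mean therefore exceeds it by d × g.

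**Type I error** when the true effect is zero = 1 − Φ(1.96 − dg/0.0962) + Φ(−1.96 − dg/0.0962).

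The documents give neither d nor g, so every row and column below is an assumption. Each cell shows the bias in SD, with type I error at n=432 in brackets.

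| Share of P+ removed | g = 0.25 | g = 0.5 | g = 1.0 |
|---|---|---|---|
| 2% | 0.005 (0.050) | 0.010 (0.051) | 0.020 (0.055) |
| 5% | 0.0125 (0.052) | 0.025 (0.058) | 0.050 (0.081) |
| 6.25% | 0.016 (0.053) | 0.031 (0.062) | 0.0625 (0.100) |
| 12.5% | 0.031 (0.062) | 0.0625 (0.100) | 0.125 (0.255) |

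Against 0.35 SD, the g = 0.5 column runs from 0.010/0.35 = 3% to 0.0625/0.35 = 18%. The corner cell is 0.125/0.35 = 36%.

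These figures describe a comparison of retained children. The planned mixed model would reduce the bias to the extent that baseline, earlier ACQ scores and the dropout covariates predict the missing value.

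**Precision.** Losing 5% of P+ lowers power from 0.953 to 0.948, and losing 12.5% lowers it to 0.940. The issue is bias, not power.

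**The case against.** The strongest reply is that the clause is neutral as to arm and refers to study procedures, which P- families also have. All participants share the five data-collection points. Protocol 4.2.2 also lists vital signs, spirometry, questionnaires and review of care coordination goals at Visits 2 to 4 for everyone. P+ families have a community health worker to help them, which could reduce removals. Protocol 3.3.1 allows up to 24 months where the interventions are not finished in 12, and the SAP models late and missed measurements at their actual times. The exclusion criteria also screen out families judged likely to be non-compliant. All of this stands.

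A reader might infer that removals fall mainly on the intervention arm. The documents do not say so. The heavier P+ schedule makes it possible, but the net direction is not established.

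A reader might also infer that removed children drop out of the intention-to-treat analysis, leaving a comparison of completers. That is not the plan. Their data to dropout are used, their assignment is unchanged, and the longitudinal model includes predictors of dropout. Bias needs removal that is both differential and non-ignorable given what was observed.

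The reply does not close the gap. Neither document provides for the missing 12-month outcome to be collected, and no planned analysis tests the MAR assumption for these children.

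**Conclusion.** The gap is real and worth correcting, but its effect is conditional. A child discontinued for non-adherence loses the 12-month ACQ. This could bias the P+ v P- contrast if such removals differ by arm and are not ignorable. Assuming that 2 to 12.5% of P+ and none of P- are removed, with a 0.5 SD gap, the bias is about 0.01 to 0.06 SD and type I error at n=432 is 0.051 to 0.100, before any correction by the MAR model. The larger figures (0.125 SD and 0.255) require every expected loss in the trial to be an adherence removal in P+, with a full 1 SD gap. If the clause is rarely used, the effect is negligible. The documents do not support saying that the intention-to-treat comparison fails. The effect on the school contrast is less clear, because most school activities are delivered by school staff or the school community health worker.

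**What to change.** Amend Protocol 4.6 and SAP 5.4 to separate two events: ending participation in intervention activities, and ending follow-up. State that non-adherence does not end the scheduled ACQ, the two-week recall or outcome abstraction from the electronic health record, unless the family withdraws consent. State that these children are analysed as randomised. Report investigator-initiated discontinuations by arm with reasons. Add a missing-not-at-random sensitivity analysis to the SAP, for example a delta adjustment applied to discontinued children over a stated range. None of this alters clinical care.

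The cost is a few follow-up contacts, of a kind already scheduled for every child at 3, 6, 9 and 12 months, with families who may be hard to reach. At the Protocol's payment rates, a child discontinued just after baseline would need at most 3 × $25 + $45 = $120 in participant payments. The documents show no staff budget for contacts after discontinuation. For children already discontinued, by-arm reporting and the sensitivity analysis remain possible.

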# 4.6.1 Early Termination Study Visit

If participants withdraw prior to completing the study, all previously collected data will be stored and used for analysis.

### 5 STUDY EVALUATIONS AND MEASUREMENTS

### 5.1 Individual Participant Measures

- Children will be measured for **height and weight** (using standard scales and stadiometers), **blood pressure**, **pulse**, **temperature**, and **pulse oximetry** (SpO2) at baseline, 3, 6, 9, and 12 months following enrollment. This information may also be abstracted from the medical record.
- Pulmonary function tests (spirometry) will be abstracted from the electronic health record if possible. If spirometry is not completed by the child's healthcare team as a part of usual clinical care, it will be completed by a trained community health worker at baseline, 3, 6, 9 and 12 months post-enrollment. Each recording will be printed out to become a part of the child's medical record. Pulmonary function testing completed for clinical purposes within one month before or after a baseline or

- follow-up study visit will be abstracted from the medical record if testing is unable to be completed at the time of a study visit.
- Juniper's **Asthma Control Questionnaire** is a validated survey and will be administered by a member of the research team to the parent/caregiver by reading out loud to avoid any literacy barriers. This will be administered at baseline, 3 months, 6 months, 9 months and 12 months
- A home **environmental assessment** will be conducted by a CHW in the living room and child sleeping area to note common triggers such as dust, pests, pets, mold and tobacco smoke measured at Home Visits 1, 2, 3, and 4.
- CAPP's **asthma knowledge survey** will be used to assess knowledge at home visits before, during and after the primary care intervention. This survey may be administered out loud to the parent/caregiver to avoid any literacy barriers.
- CHW will ask parent/caregiver for a 2-week recall of daytime cough or wheeze, nighttime cough or wheeze, missed school days, missed parent workdays at the time of the visit. This will be recorded on a tracking form in REDCap.
- The Caregiver Needs Assessment will be administered to the parent/caregiver at the baseline visit. The needs assessment is a validated instrument that focuses on the caregiver's knowledge about asthma avoidance measures and their comfort level with managing their child's asthma. For participants receiving the primary care intervention, this tool will assist the primary care community health worker with tailoring the educational component of the program to fit the needs of the individual family.
- Adverse Event Forms will be completed as needed throughout study participation.

### 5.2 Group Level Primary care and School Measures

- A REDCap tracking form will be used for documentation of time, date and dose of medication dispensed in **School Based Asthma Therapy**. This information will be collected and recorded by the school CHW.
- A **classroom environmental assessment** form will be completed by the school CHW at baseline and at end of semester for study participant classrooms.
- As a part of the Open Airways for Schools Curriculum, an **Open Airways Quiz** will be administered at the beginning and end of a school asthma management class series.
- Fidelity to the school EBI's will be monitored via observation by study research staff utilizing yes/no completion checklists of core components of each intervention.
   These checklists include the MDI checklist, OAS lesson plan and classroom environmental survey once each semester. It is expected that 90% of the core components will be implemented for maintenance of fidelity to the intervention.

